6.2.3. Study Period

Assessments and events will be classified according to the time of occurrence relative to the study treatment period.

Study treatment period for Exacerbation

Treatment period	Definition
Pre-Treatment	Event start date < IP start date
On-Treatment	Subjects who did not withdraw early from IP: Event onset date is on/after IP start date & on/before the end of analysis period. (IP Start Date \leq Event Start Date \leq end of analysis period) Subjects who withdrew early from IP: Event onset date is on/after IP start date & on/before the earlier of the IP stop date+28 days/end of analysis period. (IP Start Date \leq Event Start Date \leq IP Stop Date + 28 days/end of analysis period)
Off-Treatment	Event onset date is after IP stop date +28 days and on/before the end of analysis period. (IP Stop Date + 28 days < Event Start Date \leq end of analysis period)
Post-Treatment	Event onset date is after the end of analysis period. (Event Start Date > end of analysis period)

Note: the IP stop date is missing or the event start date is missing then the event considered on-treatment

Study Treatment Period for Visit Based Efficacy Assessments

Applicable to all visit-based efficacy assessment such as FEV1, SGRQ, ACQ, Subject Rated Response to Therapy, Clinician Rated Response to Therapy.

Treatment period	Definition
Pre-Treatment	Visit date < IP start date
On-Treatment	Subjects who did not withdraw early from IP: Visit date is after IP start date & on/before the end of analysis period. (IP Start Date < Visit Date \leq end of analysis period) Subjects who withdrew early from IP: Visit date is after IP start date & on/before earlier of the IP stop date +28 days/end of analysis period. (IP Start Date < Visit Date \leq earlier of IP Stop Date + 28 days/end of analysis period)
Off-Treatment	(IP Stop Date + 28 days < Visit Date \leq end of analysis period)
Post-Treatment	Visit Date > end of analysis period

Study treatment Period for Adverse Events

Treatment period	Definition
Pre-Treatment	Event start date < IP start date
On-Treatment	IP start date \leq Event start date \leq IP stop date +28 days
Post-Treatment	Event start date > IP stop date +28 days

Note: the IP stop date is missing or the event start date is missing then the event considered on-treatment

Study Treatment Period for Visit Based Safety Assessments

Applicable to all safety assessment such as vital signs, ECG, laboratory assessments:

Treatment period	Definition
Pre-Treatment	Visit date < IP start date
On-Treatment	IP start date \leq Visit date \leq IP stop date +28 days
Post-Treatment	Visit date > IP stop date +28 days

Study Treatment Period for Concomitant Medications

Treatment period	Definition
Pre-Treatment	Concomitant medication (CM) start date < IP start date
On-Treatment	IP start date \leq CM start date \leq IP stop date +28 days
Post-Treatment	CM start date > IP stop date +28 days

Note: the IP stop date is missing and CM start date is on/after IP start date then CM considered on-treatment
 If CM start date is missing then CM considered on-treatment

6.2.4. Length of Time in Phase for Exacerbations

The length of time in a phase reflects for each subject the period of time over which exacerbation data has been recorded and included in the negative binomial analysis model. The analysis model will incorporate this information as an offset of loge (length of time (years) in phase).

Length of time (years) will be calculated as Length of time (Days)/365.25.

The length of time a subject contributes information in each phase is detailed below.

Phase	Length of time (Days) in Phase
On- and Off-treatment	(Date of End of Analysis Period – IP Start Date) +1
On-treatment	Subjects who did not withdraw early from IP: (Date of End of Analysis Period – IP Start Date) +1 Subjects who withdrew early from IP: (IP Stop Date – IP Start Date) +28+1
Off-treatment	Subjects who did not withdraw early from IP: 0 days Subjects who withdrew early from IP: Date of End of Analysis Period – [IP Stop Date + 28 days]

Subjects who withdraw early from the study with an analysis period which ends prior to Day 372 will be considered to have missing data for a period of time calculated as: (Day 372-Date of End of Analysis Period) +1.

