4. STUDY DESIGN

4.1. Overall Design

This study employs a multi-centre, randomized, placebo-controlled, double-blind, parallel-group design ([Figure 1](#)). In the main study, there will be a total of 16 clinic visits conducted on an outpatient basis. A pre-screening visit (V0) will be conducted to sign the informed consent form (ICF) and review demography, asthma history and concomitant medications. Once the ICF is signed the subject will be assigned a subject identifier. Subjects who meet the eligibility criteria at Screening (Visit 1) will complete a 1 to 4 weeks run-in period followed by a double-blind 52-week treatment period. The run-in period is designed to capture baseline eDiary data. Subjects who experience an asthma exacerbation during the run-in should receive treatment for their exacerbation and remain in the run-in period until the subject has returned to their baseline asthma status for at least one week. Those subjects that are not able/eligible to be randomized at the end of the 4-week run-in period will be deemed run-in failures. Clinic visits will be at Pre-screening (Visit 0), Screening, Randomization (Day 1, Week 0), then every 4 weeks during treatment period until the Exit Visit at Week 52. The Exit Visit (Visit 15) represents the last day of study (i.e. 4 weeks after the last dose given at Visit 14). If a subject withdraws from this study, an early withdrawal visit (Visit Early Withdrawal [VEW]) will be performed within 4 weeks after the last dose ([Section 5.5](#)). The total duration of subject participation in the main study, including run-in will be 53 to 56 weeks. Subjects will remain on their current maintenance therapy throughout the run-in and double-blind treatment administration periods.

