5.5. Withdrawal/Stopping Criteria

Withdrawal from study treatment

Subjects may be withdrawn from study treatment at anytime by the Investigator if it is considered to be detrimental for them to continue in study treatment.

A subject must be withdrawn from study treatment if any of the following stopping criteria are met:

- Liver Chemistry: Meets any of the protocol-defined liver chemistry stopping criteria (Section 5.5.1)
- QT: Meets any of the protocol-defined stopping criteria (Section 5.5.2)
- Pregnancy: Positive pregnancy test

Other reasons for withdrawal can include: an adverse event (including abnormal liver function test other than stopping criteria or abnormal laboratory results), Investigator unblinded study treatment, clinically significant abnormality identified on ECG reading other than stopping criteria, lost to follow-up, protocol violation, lack of efficacy, sponsor terminated study, non-compliance, or for any other reason.

Subjects who withdraw from study treatment prematurely (for any reason) should, where possible, continue to be followed-up as per protocol until the completion of the Exist Visit assessments. If this is not possible, the Investigator must encourage the subject to participate in as much of the study (scheduled visits and activities, record eDiary data) as they are willing (or able) to. If subject cannot attend the visit on site, telephone contact is acceptable to collect below information: asthma exacerbation, AE/SAE, concomitant medication and to encourage subjects continue to record eDiary data.

Withdrawal from the study

Subjects are also free to withdraw consent to participate in the study at anytime. Every effort should be made to have them return to the clinic for an Early Withdrawal Visit and to return all study related materials. In those instances where the subject specifies the reason for withdrawal of consent, this information will be captured in the eCRF. Patients will not be followed for any reason after consent has been withdrawn.

A subject should only be designated as lost to follow-up if the site is unable to establish contact with the subject after 3 documented attempts via 2 different methods (phone, text, e-mail, certified letter, etc).

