6.2.2. Analysis Period for Exacerbations and Efficacy Endpoints

The analysis period defines the period of time over which exacerbations and efficacy assessments will be included in the on and/or off-treatment phases. The start and end of the analysis period is defined for subjects based on their study completion status as follows:

Study Completion	Start Date of Analysis Period	End Date of Analysis Period
Completed	First dose of investigational product (Day 1)	Earlier of Date of Week 52 visit or Date of last dose at Week 48 +35 days [1]
Withdrew early	First dose of investigational product (Day 1)	Earlier of Date reported on the study conclusion page or Date of last dose at Week 48 +35 days [1]

[1] Based on protocol Section 4.1, the Exit Visit (Visit 15) represents the last day of study (i.e. 4 weeks after the last dose given at Visit 14), allowing for the ± 7 days visit window, date of last dose at week 48+35 days is defined as the upper bound of 7 days visit window for the date of last dose at week 48+28 days.

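### The exposure offset in SAP 6.2.4 lacks the end-of-analysis-period cap that SAP 6.2.3 puts on on-treatment exacerbations (minor)

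*SAP*

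**What the plan says.** Three consecutive SAP sections define the count and the exposure for the exacerbation models.

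- **End of the analysis period (SAP 6.2.2).** For a subject who withdraws early from the study it is: "Earlier of Date reported on the study conclusion page or Date of last dose at Week 48 +35 days".
- **Which events count (SAP 6.2.3).** For a subject who withdrew early from IP, an exacerbation is on-treatment if: "Event onset date is on/after IP start date & on/before the earlier of the IP stop date+28 days/end of analysis period".
- **How much time counts (SAP 6.2.4).** The length is described as "the period of time over which exacerbation data has been recorded and included in the negative binomial analysis model". The on-treatment row for these subjects reads: "Subjects who withdrew early from IP: (IP Stop Date – IP Start Date) +28+1". The end of the analysis period appears in the other rows of that table but not in this one.

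SAP 4.2.1 pairs the on-treatment count with the log of time on treatment as offset. The resulting log rate ratio and standard error are the China inputs to the Bayesian update.

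The protocol foresees exit soon after a dose. Section 4.1 says "an early withdrawal visit (Visit Early Withdrawal [VEW]) will be performed within 4 weeks after the last dose", and Section 5.5 says "Patients will not be followed for any reason after consent has been withdrawn". For subjects who stop treatment only, Section 5.5 asks that they "continue to be followed-up as per protocol until the completion of the Exist Visit assessments".

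**The concern.** Count and exposure should cover the same days. For anyone whose follow-up ends less than 28 days after the last dose, the count stops at study exit while the exposure runs on to the last dose plus 28 days. The extra days dilute the rate in the arm where they fall.

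The offset feeds the primary rate ratio. The hospitalisation/ED and hospitalisation rates (SAP 4.3.2) and the rate of all exacerbations (SAP 4.4) reuse the method. Excess exposure mainly on placebo pushes the rate ratio up, which is towards 1 when the ratio is below 1. Excess mainly on mepolizumab pushes it down, towards benefit. Balanced excess largely cancels.

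**Working it through.** **Step 1: the mismatch in days.** Take IP stop as the date of the last dose, as the exposure formula in SAP 4.5.1 implies. Write E for the end of the analysis period.

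- Time in which events can count: min(IP stop + 28, E) - IP start + 1
- Time in the offset: IP stop - IP start + 29
- Excess: max(0, IP stop + 28 - E), so 0 to 28 days

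Example with the first dose on Day 1 and the last dose on Day 85:

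| Study conclusion | Offset, 6.2.4 | Countable time | Excess | Off-treatment length, 6.2.4 |
|---|---|---|---|---|
| Same day | 113 | 85 | 28 (+33%) | -28 |
| 14 days later | 113 | 99 | 14 (+14%) | -14 |
| 28 days later | 113 | 113 | 0 | 0 |
| 60 days later | 113 | 113 | 0 | 32 |

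In the first two rows the on-treatment length exceeds the combined on- and off-treatment length in the same table (85 and 99 days). The total balances only because off-treatment time is negative. For early study withdrawals, the last sentence of 6.2.4 also treats time after the analysis period as missing, so the excess days are both exposure and missing data.

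**Step 2: calibration.** The plan gives no figure for this offset. Its design figures serve to check the inputs, using Var(log RR) = (1/n)(1/rate_P + 1/rate_T + 2k) with n = 128, rates 0.975 and 0.585, k = 1.6, and the SAP 4.2.1 mixture posterior. Power is 66.0% (stated 66%). The largest observed rate ratio that still succeeds is 0.776 to 0.777 (stated 0.776). Success at a 40% reduction is 88.4% to 88.9% (stated 88.6%). The ranges come from using 0.975/0.585 or 0.78 in both arms for the standard error.

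**Step 3: effect on the rate ratio.** Assumptions: 150 per arm, the same rates and k, doses every 28 days, 365 days for completers. Counts were generated over the countable time, and the two-arm negative binomial model was fitted by expected log-likelihood with each offset. The table shows the shift in log rate ratio (6.2.4 offset minus capped offset). Timing patterns:

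- (i) exit 21 to 35 days after the last dose, last dose 1 to 12 (mean excess 1.9 days)
- (ii) exit on days 0 to 27, last dose 1 to 12 (mean 14.5)
- (iii) as (ii), last dose 1 to 3
- (iv) exit on the day of the last dose, last dose 1 to 12 (28)
- (v) as (iv), last dose 1 to 3

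| Leavers | i | ii | iii | iv | v |
|---|---|---|---|---|---|
| 22 per arm | +0.0001 | +0.001 | +0.002 | +0.002 | +0.005 |
| 15, placebo only | +0.0008 | +0.006 | +0.009 | +0.012 | +0.017 |
| 15, mepolizumab only | -0.0007 | -0.006 | -0.007 | -0.011 | -0.014 |
| 44, placebo only | +0.0025 | +0.020 | +0.030 | +0.038 | +0.059 |
| 44, mepolizumab only | -0.0023 | -0.018 | -0.025 | -0.035 | -0.049 |

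With 22 leavers per arm the placebo rate is 0.1% to 2.6% too low, but the ratio hardly moves. Five leavers in one arm give at most +0.005 or -0.004. A separate simulation of pattern (iv) with 44 leavers in one arm gave +0.039 and -0.035.

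**Step 4: yardstick.** The sum 1/0.975 + 1/0.585 + 3.2 is 5.935. The standard error is sqrt(5.935/128) = 0.215, or sqrt(5.935/150) = 0.199 at 150 per arm. Fifteen leavers in one arm with the worst timing shift the estimate by 0.017/0.199, or 0.09 standard errors. An observed ratio exactly at the 0.776 threshold has posterior probability 95.0%. A 1% shift takes that to 94.4% or 95.6%, and a 2% shift to 93.7% or 96.1%.

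**The case against.** - **The governing text already implies the cap.** SAP 6.2.2 opens by saying the analysis period bounds both phases, and 6.2.4 opens with the right principle. That is true, but the table row is the explicit formula, and programming it as written gives the wrong length.
- **Time on treatment may mean 28-day dose coverage, and comparability with MEA115588 may call for it.** SAP 4.5.1 uses the same formula for safety exposure. For exacerbations, however, 6.2.4 defines length by data recorded and 6.2.3 caps the events. The documents do not show how the MEA115588 offset was derived, so this stays open and affects only what is reported alongside.
- **Few subjects will be affected.** This is fair. Protocol 5.5 asks for follow-up after stopping treatment, and the 44 extra subjects are planned for treatment withdrawals (SAP 5.2), not study exits. A 28-day excess needs exit on the day of the last dose. A subject who leaves at a scheduled visit without dosing has about 7 excess days at most if the ±7-day window is measured from the preceding dose, or up to 14 if windows are anchored at randomization. The protocol does not state the anchor.
- **Some events on the excess days could still count.** The note in SAP 6.2.3 treats events with a missing start date, or a missing IP stop date, as on-treatment. This narrow exception stands.
- **The negative off-treatment length is harmless.** Agreed: no model described in the plan uses it.

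**Conclusion.** The point holds as a minor derivation error. SAP 6.2.3 and 6.2.4 give different windows for the count and the exposure of the same subjects, with an excess of 0 to 28 days for those who leave the study within 28 days of the last dose. Subjects followed for 28 days or longer after IP stop are handled correctly.

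The likely effect is at the low end of the illustrations: close to zero if leavers are balanced, and under 0.1 standard errors even with 15 leavers all in one arm. The 44-in-one-arm rows are deliberate extremes, and none of the figures is a bound. All rest on assumed numbers, timing and split of leavers, which the documents do not give. The direction cannot be known while the study is blinded, and the error could change the conclusion only for a result very near the success threshold. The stated power and success probabilities are not affected.

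**What to change.** In SAP 6.2.4, for subjects who withdrew early from IP:

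- On-treatment length = min(IP Stop Date + 28, Date of End of Analysis Period) - IP Start Date + 1
- Off-treatment length = max(0, Date of End of Analysis Period - (IP Stop Date + 28))

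This carries SAP 6.2.3's own limit into the offset. It costs a small wording change in one table and the matching derivation code, needs no new data, and should be made before unblinding. The sponsor should check how the MEA115588 offset was derived. If it was uncapped, report the uncapped version as a comparability check.

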6.2.5. Study Day and Reference Dates

The safety reference date is the study intervention start date and will be used to calculate study day for safety measures.

The efficacy reference date is the date of the study intervention start date and will be used to calculate study day for efficacy measures and baseline characteristics, as well as efficacy durations.

The study day is calculated as below:

Assessment Date = Missing → Study Day = Missing

Assessment Date < Reference Date → Study Day = Assessment Date – Ref Date

Assessment Data ≥ Reference Date → Study Day = Assessment Date – Ref Date + 1

6.2.6. Assessment Window

Clinic visits are scheduled to take place as specified in the protocol. Measurements outside visit windows will not be excluded from analyses on any population. For all clinic visits, nominal visit days and times will be used for reporting, such that if a subject recorded values on the Week 4 visit that were actually made on Week 3 of treatment, they will be presented as Week 4 values.

If a subject withdraws at a scheduled visit, and these data were scheduled to be collected at that visit, the data will be summarised and analysed (as appropriate) together with data from subjects who did not withdraw. If a subject withdraws at a scheduled visit at which these data were not scheduled to be collected, or if a subject withdraws between scheduled visits, data will be slotted to the next visit where the data was scheduled to be collected according to the study flowchart. The protocol visit windows of ± 7 days should be applied to the assignment of withdrawal visits, so that if a subject withdraws within the appropriate number of days from the last visit where that data was scheduled to be collected, they would get that data slotted to that visit and otherwise the data will be slotted to the next scheduled visit. The early withdrawal visit will then be re-labelled as the corresponding visit.

For unscheduled visits, excluding a subject's baseline visit (where IP is initiated) or exit visit, the same logic will be applied. If a subject has an unscheduled assessment within the appropriate number of days (± 7 days) from a visit where that data was scheduled to be collected, this data would be slotted to that visit and otherwise the data will be slotted to the next scheduled visit. Liver event and log visits will be excluded from summary tables, but included in the 'any time post baseline' data.

If there is more than one assessment associated with a particular visit interval then the closest assessment will be used for summary tables and analyses. Where two or more ECG findings slot to the same visit interval, the most 'abnormal' results will be used, i.e. according to the following hierarchy: Abnormal-Clinically Significant > Abnormal – not clinically significant > Normal.

6.2.7. Multiple measurements at One Analysis Time Point

When triplicate ECG assessments are taken, mean of the measurement will be calculated first and summary statistics will be based on the calculated mean. This will apply to both baseline and post baseline assessments.

For lab tests on a study day, if more than one assessment is taken on the same day, the test from a central lab will be taken over the test from a local lab. If multiple assessments are taken from the same type of lab, the worst case will be used.

6.2.8. Handling of Partial Dates

Element	Reporting Detail
General	
 Partial dates will be displayed as captured in participant listing displays. However, where necessary, display macros may impute dates as temporary variables for sorting data in listings only. In addition, partial dates may be

Element	Reporting Detail				
	
imputed for ‘slotting’ data to study phases or for specific analysis purposes as outlined below.
 
 • Imputed partial dates will not be used to derive study day, time to onset or duration (e.g., time to onset or duration of adverse events), or elapsed time variables (e.g., time since diagnosis). In addition, imputed dates are not used for deriving the last contact date in overall survival analysis dataset. 				
Adverse Events	
 • Partial dates for AE recorded in the CRF will be imputed using the following conventions: 
 
 Missing start day	 
If study intervention start date is missing (i.e. participant did not start study intervention), then set start date = 1st of month.
 
Else if study intervention start date is not missing:
 
 ○ If month and year of start date = month and year of study intervention start date, then 
 ▪ If stop date contains a full date and stop date is earlier than study intervention start date, then set start date= 1st of month. ▪ Else set start date = study intervention start date. 
Else set start date = 1st of month.
 	
 
 Missing start day and month	 
If study intervention start date is missing (i.e. participant did not start study intervention), then set start date = January 1.
 
Else if study intervention start date is not missing:
 
 ○ If year of start date = year of study intervention start date, then 
 ▪ If stop date contains a full date and stop date is earlier than study intervention start date, then set start date = January 1. ▪ Else set start date = study intervention start date. 
Else set start date = January 1.
 	
 
 	Missing start day	
If study intervention start date is missing (i.e. participant did not start study intervention), then set start date = 1st of month.
 
Else if study intervention start date is not missing:
 
 ○ If month and year of start date = month and year of study intervention start date, then 
 ▪ If stop date contains a full date and stop date is earlier than study intervention start date, then set start date= 1st of month. ▪ Else set start date = study intervention start date. 
Else set start date = 1st of month.
	Missing start day and month	
If study intervention start date is missing (i.e. participant did not start study intervention), then set start date = January 1.
 
Else if study intervention start date is not missing:
 
 ○ If year of start date = year of study intervention start date, then 
 ▪ If stop date contains a full date and stop date is earlier than study intervention start date, then set start date = January 1. ▪ Else set start date = study intervention start date. 
Else set start date = January 1.

Missing start day	
If study intervention start date is missing (i.e. participant did not start study intervention), then set start date = 1st of month.
 
Else if study intervention start date is not missing:
 
 ○ If month and year of start date = month and year of study intervention start date, then 
 ▪ If stop date contains a full date and stop date is earlier than study intervention start date, then set start date= 1st of month. ▪ Else set start date = study intervention start date. 
Else set start date = 1st of month.
				
Missing start day and month	
If study intervention start date is missing (i.e. participant did not start study intervention), then set start date = January 1.
 
Else if study intervention start date is not missing:
 
 ○ If year of start date = year of study intervention start date, then 
 ▪ If stop date contains a full date and stop date is earlier than study intervention start date, then set start date = January 1. ▪ Else set start date = study intervention start date. 
Else set start date = January 1.
				

Element	Reporting Detail	
	Missing end day	A '28/29/30/31' will be used for the day (dependent on the month and year).
	Missing end day and month	No Imputation
	Completely missing start/end date	No imputation
Concomitant Medications/ Medical History	
 Partial dates for any concomitant medications recorded in the CRF will be imputed using the following convention: 	
	Missing start day	
If study intervention start date is missing (i.e. participant did not start study intervention), then set start date = 1st of month.
 
Else if study intervention start date is not missing:
 
 If month and year of start date = month and year of study intervention start date, then 
 If stop date contains a full date and stop date is earlier than study intervention start date, then set start date= 1st of month. Else set start date = study intervention start date. 
Else set start date = 1st of month.

	Missing start day and month	
If study intervention start date is missing (i.e. participant did not start study intervention), then set start date = January 1.
 
Else if study intervention start date is not missing:
 
 If year of start date = year of study intervention start date, then 
 If stop date contains a full date and stop date is earlier than study intervention start date, then set start date = January 1. Else set start date = study. intervention start date.

Element	Reporting Detail	
		Else set start date = January 1.
	Missing end day	A '28/29/30/31' will be used for the day (dependent on the month and year).
	Missing end day and month	A '31' will be used for the day and 'Dec' will be used for the month.
	Completely missing start date	No imputation
	Completely missing end date	The date of last visit for this participant will be used

